### **Statistical analysis**

The study analysis will be performed on a modified intention-to-treat basis: All patients who were randomised and received at least 1 dose of the study medication will be included in the analysis.

Baseline and demographic characteristics will be presented using descriptive statistics. Continuous data will be expressed as means and standard deviations, or medians and interquartile ranges (IQR), depending on variable distribution. The normality of variable distribution will be assessed by exploratory data analysis, including histograms and boxplots. Differences in continuous data between groups will be assessed using a parametric t-test or Mann-Whitney U test, as appropriate. Categorical data will be presented as frequencies and proportions and analysed using a Chi-square test. If expected cell counts are small (less than 5), Fisher's exact test will be used instead. For all analyses, a two-sided p-value of less than 0.05 will be considered statistically significant. All analyses will be conducted under the supervision of a statistician blinded to intervention group assignment. Experienced study staff will perform data analysis in collaboration with biostatisticians using statistical Stata version 13 (StataCorp LLC, College Station, TX) or later.

#### *Analysis of primary and secondary outcomes*

A parametric t-test or Mann-Whitney U test will be used, as appropriate, to determine whether time from initiation of midodrine until discontinuation of IV vasopressors, time from ICU admission to ICU discharge readiness, and ICU and hospital LOS differ between groups.

A Chi-Square or Fisher's exact test will be used to test whether rates of ICU readmission and incidence of adverse events are different between treatment groups.

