### Study population and study sites

The study will enrol patients admitted to an intensive care or high-dependency unit (ICU/HDU) and meeting all eligibility criteria detailed in the study protocol. Study sites include Massachusetts General Hospital (Boston, MA, USA), Sir Charles Gairdner Hospital (Perth, Australia), and Beth Israel Deaconess Medical Center (Boston, MA, USA).

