### Randomisation

Patients will be randomly allocated in a 1:1 ratio to receive either midodrine or placebo. Randomisation will be performed using a computer-generated randomisation list and will be stratified by study site. Randomisation lists will be created by an independent, unblinded study team member, under the supervision of an independent statistician. The randomisation list will be provided directly to the research pharmacy, which will be responsible for preparing and dispensing the study medications following an active order for study medications. This includes preparation and blinding of the placebo in accordance with the study randomisation schema.

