### Outcomes

- *Primary endpoint:*
  - Time until discontinuation of IV vasopressors, measured in hours from initiation of midodrine until discontinuation of IV vasopressors
- *Secondary endpoints:*
  - Time to ICU discharge readiness, defined as the number of days from study drug initiation to meeting discharge criteria
  - ICU length of stay, defined as the number of days in the ICU prior to transfer to the general floor
  - Hospital length of stay, defined as the total number of days in the hospital after first study drug administration
  - Rates of ICU readmission, defined as the number of patients readmitted back to the ICU after prior discharge to the general floor
- *Safety endpoints:*
  - Hypertension (increase in blood pressure to a systolic blood pressure (SBP) 20 percent higher than the predefined goal set by the primary team), bradycardia (decrease in heart rate 20 percent lower than the predefined goal set by the primary team), hemodynamically significant tachyarrhythmia (>20 percent decrease in systolic blood pressure).

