### **Sample size estimation**

The sample size estimation is informed by the previous observational study by Levine et al. In this study, the rates of vasopressor administration decreased by 38% from  $-0.62 \pm 1.40$  mcg/min per hour to  $-2.20 \pm 2.45$  mcg/min per hour after addition of midodrine. Based on a median time of 17 h from midodrine initiation to discontinuation of IV vasopressors, the 38% reduction translates to an estimated 6 h difference. 6 h is also thought to be a meaningful time frame in terms of reduction in duration of vasopressor treatment. Accordingly, we expect that a sample size of 50 subjects per group will provide us with >80% probability (power) to detect a difference of 6 h in the primary outcome. Allowing for drop-out, our target sample size is 120.

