### **Statistical Analytical Issues**

Multiple Comparisons: There will be no adjustment for multiple testing. Results of secondary outcomes and post hoc analyses will therefore be considered exploratory.

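### Randomisation is stratified by site but the primary test ignores site; adding it is a cheap efficiency gain of unknown size, possibly zero or slightly negative

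*Combined protocol and SAP*

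**What the plan says.** In the SAP, Randomisation: "Patients will be randomly allocated in a 1:1 ratio to receive either midodrine or placebo", and "Randomisation will be performed using a computer-generated randomisation list and will be stratified by study site". Study population and study sites names three sites, two in Boston and one in Perth. No section gives a planned number per site or says whether the lists are blocked.

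The primary endpoint (SAP, Outcomes) is "Time until discontinuation of IV vasopressors, measured in hours from initiation of midodrine until discontinuation of IV vasopressors". Under Analysis of primary and secondary outcomes, "A parametric t-test or Mann-Whitney U test will be used, as appropriate", for this endpoint and for discharge readiness, ICU stay and hospital stay. The choice between the two tests rests on inspecting the data (SAP, Statistical analysis): "The normality of variable distribution will be assessed by exploratory data analysis, including histograms and boxplots". Neither test has a site term. No covariate, stratified test or site-adjusted sensitivity analysis appears elsewhere, and the protocol's own Statistical Analysis section only refers to the SAP.

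**The concern.** The design treats site as worth controlling at allocation, and the analysis then sets it aside. If the lists are balanced within site and sites differ in typical vasopressor duration, the between-site variation is removed from the treatment comparison but stays in the standard error of an unstratified test. The test then rejects less often than it could. If the lists are not balanced within site, chance differences in site mix add noise that an adjusted analysis would remove.

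What is at stake is some power in a trial of about 100 evaluable patients, recoverable without new data because site is already a randomisation stratum. Timing matters. A site-adjusted analysis added after the results are known would fall under the SAP's provision that "Results of secondary outcomes and post hoc analyses will therefore be considered exploratory".

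**Working it through.** **1. The plan's own figure.** Sample size estimation says "a sample size of 50 subjects per group will provide us with >80% probability (power) to detect a difference of 6 h". No SD is given, so the power cannot be reproduced; it can only be inverted. At exactly 80% power and two-sided 5%, the noncentrality is 1.960 + 0.842 = 2.802, so SD = 6 × √25 / 2.802 = 10.7 h. More than 80% power means a smaller SD; 90% gives 6 × 5 / 3.242 = 9.25 h.

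**2. Formulas, allocation balanced within site.** Let R² be the share of outcome variance due to site (assumed; the documents give none) and nc = 2.802.

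- t-test type I error = 2 × (1 − Φ(1.96 / √(1−R²)))
- t-test power = Φ((nc − 1.96) / √(1−R²))
- power with site in the model = Φ(nc / √(1−R²) − 1.96)

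Example, R² = 10%: √0.9 = 0.949. The t-test has Φ(0.842/0.949) = 81.3%. The adjusted model has Φ(2.802/0.949 − 1.96) = 84.0%.

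| R² | t-test type I error | t-test power | With site | Gain (points) |
|---|---|---|---|---|
| 0% | 5.0% | 80.0% | 80.0% | 0 |
| 5% | 4.4% | 80.6% | 82.0% | 1.4 |
| 10% | 3.9% | 81.3% | 84.0% | 2.7 |
| 20% | 2.8% | 82.7% | 87.9% | 5.3 |

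Gains are taken before rounding. With SD 9.25 h they are 0, 0.8, 1.6 and 2.8 points.

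**3. Simulation.** Inputs: N = 100, sites 34/33/33 with evenly spaced means, and either permuted blocks of 4 or simple 1:1 allocation within site. The linear model is compared with the t-test on normal data (SD 10.7 h, 6 h shift). Van Elteren is compared with Mann-Whitney on lognormal data (medians 17 and 11 h, log SD 0.76, chosen so that Mann-Whitney has about 80% power). Entries are gains in points. Runs used 40,000 or 20,000 trials per cell, and a range shows two runs.

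| R² | Linear, blocks | Linear, simple | van Elteren, blocks | van Elteren, simple |
|---|---|---|---|---|
| 0% | 0.0 | −0.7 | −0.9 | −1.6 |
| 1% | +0.3 (formula) | −0.6 to −0.3 | −0.6 to −0.4 | −1.4 to −1.3 |
| 2% | not run | −0.2 to −0.1 | −0.2 to −0.1 | −0.9 to −0.8 |
| 3% | +0.8 (formula) | +0.3 to +0.4 | 0.0 | −0.3 to −0.2 |
| 5% | +1.3 | +1.1 | +0.6 | +0.4 |
| 10% | +2.8 | +3.3 | +2.1 | +2.8 |
| 20% | +5.5 | +7.6 | +5.3 | +7.4 |

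Break-even is at an R² of about 2 to 3% for the linear model under simple allocation, about 3% for van Elteren with blocks, and 3 to 5% for van Elteren with simple allocation. With blocks, the linear model costs nothing even at R² = 0. Type I error of the adjusted tests was 4.7 to 5.1% in all these cells. A 70/15/15 split with blocks gave van Elteren gains of −0.9, +0.8, +2.1 and +5.0 at R² of 0, 5, 10 and 20%.

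**4. Van Elteren in place of the t-test.** On normal data with blocks of 4 the difference was −3.0, −1.2, 0.0 and +3.4 points at R² of 0, 5, 10 and 20%. It should replace only the rank test.

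**5. Scale.** With three equal, evenly spaced sites, the gap between the extreme sites is 2 × √(1.5 × R²) × 10.7: about 6, 8 and 12 h at R² of 5, 10 and 20%. The SAP's reference median is 17 h.

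**The case against.** The strongest reply is that nothing is broken and that the sign of the change is uncertain. Every gain rests on an assumed R² and a back-solved SD. Gains of 3 points or more need sites that differ by 8 h or more, which exceeds the 6 h treatment effect, and nothing in the documents shows such a gap. The endpoint is a duration that the SAP summarises by a median, so the rank path may well be the one used, and there van Elteren loses power when sites differ little. No blocking is stated, so the less favourable simple-allocation results cannot be set aside.

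All of this stands, and it limits the point to an optional improvement. It does not remove it: the losses are bounded at under 2 points, while the gains reach 5 to 8 points if sites differ materially.

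Three stronger readings are tempting, and the documents support none of them:

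- **The unstratified test is invalid.** It is not. With balanced allocation its type I error is at or below 5%; with simple allocation it stays near 5%.
- **The trial misses its planned power because site is omitted.** Under balanced allocation the t-test formula gives 80.0 to 82.7%. The loss is only relative to an adjusted test.
- **Adjustment always helps when site is prognostic.** The rows for R² of 1 to 3% show otherwise, except for the linear model with blocked lists.

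**Conclusion.** The mismatch between a site-stratified design and an analysis without site is real and is settled by the text. Its cost is not: the documents give no SD, between-site variance, per-site numbers or blocking method. The gain is therefore unknown. It is roughly 1 to 3 points of power at a site share of 5 to 10%, and 5 to 8 points at 20%, under the stated assumptions. It is nil or slightly negative if site explains less than about 2 to 5% of the variance. If the planned power is well above 80%, the gains shrink. This is a low-priority efficiency improvement, not the correction of an invalid test. The missing SD and the data-driven choice between the two tests are separate matters.

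**What to change.** Before unblinding, amend Analysis of primary and secondary outcomes in the SAP:

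- Keep the planned choice between a parametric and a rank analysis, and include site in each path. Where the t-test would be used, fit a linear model with treatment and site. Where Mann-Whitney would be used, apply the van Elteren test stratified by site.
- Report the unstratified test as a sensitivity analysis.
- Treat discharge readiness, ICU stay and hospital stay the same way; they remain exploratory.
- State under Randomisation whether the lists are blocked within site.

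Site-stratified tests for readmission and adverse events are optional; no gain was computed for them.

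The cost is SAP wording and minor programming, with no new data. If sites differ little, the price in power is 0 to about 1 point for the linear model. For van Elteren it is up to about 1 point with blocked lists, or about 1.7 points with simple allocation.

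### The primary test is left open between two tests that both ignore the site strata; naming one site-stratified rank test in advance costs almost nothing and protects power if sites differ

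*Combined protocol and SAP*

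**What the plan says.** The SAP (Outcomes) defines the primary endpoint as "Time until discontinuation of IV vasopressors, measured in hours from initiation of midodrine until discontinuation of IV vasopressors". Under Analysis of primary and secondary outcomes it gives two candidate tests: "A parametric t-test or Mann-Whitney U test will be used, as appropriate, to determine whether time from initiation of midodrine". The same sentence covers time to ICU discharge readiness and ICU and hospital LOS.

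The basis for choosing is in the Statistical analysis section: "The normality of variable distribution will be assessed by exploratory data analysis, including histograms and boxplots". No cut-off is given. The SAP does not say whether the inspection is pooled or by arm, or when it happens. That section does put all analyses under the supervision of a statistician blinded to assignment, and sets the threshold: "a two-sided p-value of less than 0.05 will be considered statistically significant".

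The SAP's Randomisation section says allocation "will be stratified by study site". There are three sites, two in Boston and one in Perth. Neither candidate test takes site into account.

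On power, Sample size estimation states that "a sample size of 50 subjects per group will provide us with >80% probability (power) to detect a difference of 6 h". It does not say which test this refers to, and it gives no SD or distribution for the time in hours.

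**The concern.** A trial should have one confirmatory test, fixed before the data are seen. Here it is picked from the outcome data by eye. The two candidates also address different quantities: the t-test compares means, Mann-Whitney compares rank ordering, and the 6 h target is derived from a median.

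Both candidates also drop the stratification factor. Stratified allocation balances the arms within site. An unstratified test still counts between-site variation as noise, so its standard error is too large for the design. What is at stake is power, together with a primary p-value whose method was not settled in advance.

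**Working it through.** **1. The plan's own power.** Inputs from Sample size estimation: difference 6 h, 50 per group; two-sided 0.05 from Statistical analysis. With the normal approximation, power = Φ(6 / (SD × √(2/50)) − 1.96), and √(2/50) = 0.2.

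- Solving for 80%: SD = 6 / (0.2 × (1.96 + 0.842)) = 10.7 h.
- SD 12 h: Φ(2.50 − 1.96) = 71%. SD 15 h: Φ(2.00 − 1.96) = 52%.

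The stated power of over 80% cannot be reproduced, because no SD in hours is given. The only SDs in that section (1.40 and 2.45) are for the rate of change of vasopressor dose.

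**2. Assumed shapes and medians.** The effect is 17 × 0.38 = 6.46 h, which the plan takes as 6 h. The text does not settle which arm the 17 h belongs to, so both 11 v 17 h and 17 v 23 h were used. Skew is likely: a normal curve with mean 11 h and SD 10.7 h would put Φ(−11/10.7) = 15% of patients below zero.

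**3. Effect of ignoring site.** Simulation of 6,000 log-normal trials per row, 60 per group, medians 11 v 17 h for power and equal medians for type I error. Site sizes and site shifts are assumed, since the documents give neither. A shift of ±0.5 on the log scale means a ratio of e^1.0 = 2.7 between the extreme sites' medians; ±0.2 means e^0.4 = 1.5. Cells show t-test / Mann-Whitney / van Elteren.

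| Site shifts | Log-SD | Power, % | Type I error, % |
|---|---|---|---|
| none | 0.75 | 79.1 / 86.8 / 86.5 | 4.3 / 4.6 / 4.7 |
| none | 1.0 | 47.5 / 63.3 / 62.6 | 4.1 / 4.9 / 4.9 |
| ±0.2 | 0.75 | 77.6 / 86.0 / 86.8 | 4.7 / 5.2 / 5.7 |
| ±0.2 | 1.0 | 46.1 / 62.4 / 62.9 | 4.0 / 4.5 / 4.7 |
| ±0.5 | 0.75 | 66.0 / 80.0 / 86.0 | 2.4 / 2.4 / 4.7 |
| ±0.5 | 1.0 | 39.6 / 57.5 / 62.7 | 3.5 / 3.7 / 5.2 |

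Simulation error is about 0.3 points for type I error (√(0.05 × 0.95 / 6000)) and 0.4 points for power near 86%. A repeat of the ±0.5, log-SD 0.75 case gave about 69%, 82% and 86%. Against unstratified Mann-Whitney in that case, van Elteren therefore gains 86 − 82 = 4 to 86 − 80 = 6 points. At ±0.2 the gain is under 1 point. With no site effect the loss is 0.3 to 0.7 points here, and under about 1.5 points across repeats.

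**4. How often the two planned tests disagree at p < 0.05.** 20,000 trials per scenario, 50 to 60 per group, a true effect present, no site effect:

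- Normal, SD 10.7 h: 4-5%.
- Log-normal, log-SD 0.5: 1% (11 v 17 h) or 7-9% (17 v 23 h).
- Log-normal, log-SD 0.75 to 1.25: 13-28%.
- Exponential: 14-18%.
- Weibull, shape 1.5: 8-13%.

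The better test depends on the shape. At 60 per group and 11 v 17 h, log-normal with log-SD 1.0 gives 48% (t-test) v 64% (Mann-Whitney); exponential gives 64% v 53%.

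**5. Type I error of the choice.** With no true effect the tests disagree in 2-6% of trials. If either significant result could be counted, type I error is 6.1-7.7%. With a Shapiro-Wilk rule standing in for the visual check (2,000 trials), it is 4.1-6.7%, with simulation error of about 0.5 points. That rule picked Mann-Whitney in 99-100% of skewed trials and about 10% of normal ones.

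**The case against.** The best defence is that the SAP has a selection rule, even if informal. When durations are clearly skewed, any reasonable look at histograms leads to Mann-Whitney. When they are near normal and the choice is truly open, the two tests agree about 95% of the time. A reader might infer that the tests conflict often enough to decide the trial, or that a t-test will cost 10 to 15 points of power. The documents do not support either: they give no distribution in hours, and followed as written the rule would nearly always avoid the t-test under clear skew. This part of the defence stands.

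A reader might also infer that type I error is about 7%. That needs both tests run and the better one kept, which nothing in the SAP allows. Blinded supervision is a partial safeguard only: a two-sided p-value is the same whichever way the arms are labelled, so blinding does not hide which test is significant.

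Nor can the t-test be excluded merely because durations are skewed, since it has more power for exponential durations. This argues for fixing the test early, because the plan never states the shape.

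On site, the defence is right that ignoring it does not inflate type I error, and that the documents report no site differences. It is also right that van Elteren does not estimate a difference in medians, so naming it settles the test but not the estimate in hours. None of this is a reason to leave the test open or to drop a factor already built into the randomisation.

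**Conclusion.** The concern holds in a limited form. The primary test is not fixed, the criterion for choosing it is visual with no cut-off, and neither option uses the site strata.

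The firmest part is the stratification. Its benefit depends on assumed site differences: 4 to 6 points of power over Mann-Whitney for a 2.7-fold spread between the extreme sites' medians, and under 1 point for a 1.5-fold spread. In the larger case the unstratified tests are conservative, with type I error of about 2-4%. The price if sites do not differ is negligible.

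The open choice of test is a weakness of pre-specification whose practical effect cannot be sized from the documents. The 1% to 28% disagreement is a range over assumed shapes, not an estimate for this trial, and 6-8% type I error is the upper case in which either result counts. This is an improvement the sponsor should make; it does not show that the planned analysis is invalid.

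**What to change.** In the SAP, under Analysis of primary and secondary outcomes, replace the choice of two tests for the primary endpoint with one, before any outcome data are examined. Suggested wording: *The primary endpoint will be compared between groups with a van Elteren test (rank-sum test stratified by study site), two-sided at the 0.05 level. The t-test and the unstratified Mann-Whitney test will be reported as sensitivity analyses only.* Apply the same stratified test to ICU LOS, hospital LOS and time to discharge readiness. State which estimate in hours will accompany the primary test.

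The cost is a short SAP edit. It needs no extra patients or data, since site is already recorded as the randomisation stratum. The downsides are the small power loss if sites do not differ, and some loss against a t-test for certain shapes: for exponential durations at 60 per group, unstratified Mann-Whitney had 53% power against 64% for the t-test, and a stratified rank test would share most of that loss.

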midodrine has been observed to effectively wean patients off continuous IV vasopressors. For patients whose only barrier to discharge from the ICU was administration of continuous medications, midodrine also appeared to decrease ICU length of stay. However, it is unknown if midodrine shortened their total hospital LOS or put the patient at risk of being readmitted back to an ICU. Additionally, midodrine appears to be well tolerated by patients when prescribed at MGH because there have been no safety reports submitted due to an adverse reaction.

No previous studies have examined the use of midodrine for the treatment of hypotension in an ICU setting. We are investigating a new indication for midodrine as the treatment for hypotension in critically ill patients. We expect that midodrine will decrease the time of patients being administered continuous vasopressors by 6 hours and therefore accelerate their readiness for ICU discharge. This has potential to have a significant impact on healthcare costs by reducing ICU and hospital LOS.

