### Data Collection

Baseline descriptive data collection will occur on day of enrolment and includes age, sex, ethnicity, APACHE II score, admission diagnosis, pre-existing co-morbidities (diabetes, coronary artery disease, asthma, peripheral vascular disease, renal failure, psychiatric disease, musculoskeletal disease, and others) obtained from the subject, the subject's family, and the subject's medical chart. Baseline laboratory data will be recorded (haemoglobin, white cell count, alanine aminotransferase (ALT), international normalised ratio (INR), bilirubin, urea, creatinine, troponin, lactate). During the study daily SOFA scores, blood pressure goals, total fluid balances, transfused red blood cell units, administered corticosteroids, use of epidural analgesia, vasopressor and study drug start and end

times will be recorded. Days between admission and discharge from the ICU and hospital will be recorded. Readmissions to the ICU during the hospital stay will be identified through daily medical record review.

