### **Post-hoc analyses**

Post-hoc data-driven analyses are allowed after the following are undertaken:

1. Document which analyses were conducted after the results for the primary and secondary outcomes are analysed.
2. Document the rationale for these analyses.
3. Pre-specify their interpretation in the context of the primary and secondary results and their impact on the overall trial conclusions.

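### The SAP defines time to ICU discharge readiness from study drug initiation but tests it from ICU admission

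*Combined protocol and SAP*

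**What the plan says.** The SAP's Outcomes section lists the secondary endpoint as "Time to ICU discharge readiness, defined as the number of days from study drug initiation to meeting discharge criteria".

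The SAP's Analysis of primary and secondary outcomes section names the quantities to be compared by t-test or Mann-Whitney test. The primary one is "time from initiation of midodrine until discontinuation of IV vasopressors". The discharge-readiness one is "time from ICU admission to ICU discharge readiness". So within a single sentence the primary endpoint runs from first dose and discharge readiness runs from ICU admission.

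The neighbouring stay endpoints are also not uniform. Hospital stay is counted after the first dose. The SAP gives "ICU length of stay, defined as the number of days in the ICU prior to transfer to the general floor", with no stated start.

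**The concern.** The defined variable and the tested variable are different quantities, and an analyst cannot follow both sections.

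ICU time before the first dose is fixed before treatment can act. With the planned unadjusted tests, including it generally adds noise to the comparison. It leaves the expected mean difference unchanged, and randomisation means that it brings no systematic bias.

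Because both starts appear in the plan, either result could be presented as pre-specified. The safeguard in the Post-hoc analyses section ("Document which analyses were conducted after the results for the primary and secondary outcomes are analysed") is aimed at analyses added later and would not obviously catch the choice.

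The endpoint is close to the trial's rationale: the background section expects midodrine to shorten vasopressor time and "therefore accelerate their readiness for ICU discharge".

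**Working it through.** **1. Do the two sections mean the same endpoint?** The analysis section covers vasopressor discontinuation, discharge readiness, ICU and hospital stay, and ICU readmission. This matches the SAP's primary and secondary endpoint list item for item. They are one endpoint with two starts, not two endpoints.

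**2. Does other text settle the start?**
- The protocol's Outcomes section omits discharge readiness.
- The protocol's Statistical Analysis section only refers to the SAP.
- The SAP's Data Collection section names no start for this endpoint.

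**3. Do the starts differ in practice?** The protocol's Subject Selection section requires more than 24 hours of failed weaning from IV vasopressors, and consent and randomisation follow. For a typical patient the two clocks differ by about a day or more, on an endpoint counted in days.

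**4. Effect on precision.** The plan gives no figure to reproduce, and no SD or correlation for these times. Let k = pre-dose SD / post-dose SD and rho = the correlation between pre-dose and post-dose time. Then

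Var(pre + post) / Var(post) = 1 + k² + 2·rho·k.

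This exceeds 1 unless rho is below -k/2. For example, k = 1 and rho = 0.3 give 1 + 1 + 0.6 = 2.60; k = 1/3 and rho = -0.3 give 1 + 0.111 - 0.2 = 0.91.

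**5. Effect of having two starts available.** The correlation between the two versions of the endpoint is (1 + rho·k) / sqrt(1 + k² + 2·rho·k). With no treatment effect, the chance that at least one of two tests has |Z| > 1.96 follows from the bivariate normal distribution.

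| Assumed k | Assumed rho | Variance factor | P(at least one p<0.05) |
|---|---|---|---|
| 1/3 | -0.3 | 0.91 | 6.6% |
| 1/3 | 0 | 1.11 | 6.5% |
| 1/3 | +0.3 | 1.31 | 6.3% |
| 2/3 | -0.3 | 1.04 | 7.9% |
| 2/3 | 0 | 1.44 | 7.6% |
| 2/3 | +0.3 | 1.84 | 7.2% |
| 1 | -0.3 | 1.40 | 8.8% |
| 1 | 0 | 2.00 | 8.3% |
| 1 | +0.3 | 2.60 | 7.8% |

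The break-even rho is -0.17, -0.33 and -0.50 for k = 1/3, 2/3 and 1. Whatever k and rho are, the either-start probability cannot exceed 2 × 5% = 10%.

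**6. Check under Mann-Whitney.** In 20,000 simulated null trials with 50 per arm, lognormal times and rho = 0, the either-start rates were 6.6%, 7.7% and 8.2% for k = 1/3, 2/3 and 1, close to the normal-theory values. This checks the error rate only, not the precision loss.

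**The case against.** The best defence is that the Outcomes section contains the only formal definition, so it governs, and the analysis wording is a drafting slip. That is the natural reading, and the fix below adopts it. The SAP does not say so, however, and the section an analyst would program from says something else.

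A second start that was tried after seeing the first result might be held to fall under the post-hoc documentation rule. That is arguable, so the rule offers some protection, but not a clear one.

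The illustration is not a bound. At k = 2 and rho = 0 the variance factor is 1 + 4 = 5 and the either-start rate is 9.2%. The variance factor describes a comparison of means and is not the efficiency measure for Mann-Whitney. Both points stand: only the direction and the 10% ceiling are general.

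The stakes are limited. Secondary results are declared exploratory without multiplicity adjustment, and four independent unadjusted secondary tests would already give 1 - 0.95⁴ = 18.5%. A blinded statistician supervises the analyses. These facts reduce the consequence but do not tell the analyst which variable to build.

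It is also fair to say that aligning the start does not complete the endpoint: the SAP's Outcomes section refers to discharge criteria that the documents do not set out, and Data Collection lists no readiness time. That is a separate gap.

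**Conclusion.** The concern holds. Two current sections of the SAP give one secondary endpoint different starts, and nothing reconciles them. As written, the analysis section tests a quantity that does not match the endpoint's definition.

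The consequence is a likely loss of precision and an open choice between two results, not bias. The size of the loss cannot be derived from the documents; the ranges shown rest on assumed values of k and rho. The primary endpoint and the sample size are untouched. The correction should be made, but the trial's main conclusion does not depend on it.

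The unstated start of ICU stay is a lesser point of clarity, not a contradiction. Its wording and the Data Collection section suggest ICU admission.

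**What to change.** In the SAP's Analysis of primary and secondary outcomes section, change the start of discharge readiness from ICU admission to study drug initiation. This matches the definition and the start of the primary endpoint. Settle it before unblinding.

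As a clarification, add a clause to the SAP's Outcomes section stating when ICU length of stay starts. If the whole ICU stay remains the tested quantity, a comparison from first dose, or one adjusted for pre-dose ICU time, can be reported alongside it and labelled as supportive; this is optional.

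The cost is one phrase and one clause. The start exists for every analysed patient, because "All patients who were randomised and received at least 1 dose of the study medication will be included in the analysis", and Data Collection already records "vasopressor and study drug start and end" times. The Confidentiality and Security section keeps dates out of REDCap, so the interval from first dose to readiness would presumably be entered as a derived number. No tested quantity other than discharge readiness changes.
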